### **9.15 Unanticipated Safety Event Reporting Requirements**

If the Investigator determines that a safety event meets the definition of unanticipated (UADE), the Investigator or their designee must notify the IRB and FDA within 10 days of becoming aware of the event.

An evaluation of a UADE will be immediately conducted and results of the evaluations will be reported to FDA and all reviewing IRBs in accordance with the applicable national and local regulations.

### **9.16 Follow-up of Safety Events**

SAE/SADE/UADEs will be followed until the event resolves, the condition stabilizes, the event is

otherwise explained, the subject is lost to follow-up or death occurs.

New or updated information will be recorded on a follow up Serious Adverse Event Report.

## **10.0 INFORMED CONSENT and RISKS**

All subjects must sign an informed consent document consistent with local institutional and Federal guidelines stating that they are aware of the investigational nature of this protocol and of the possible risks of treatment. Further, subjects must be informed that no efficacy of this therapy is guaranteed, and that unforeseen risks may occur. Full confidentiality of patients and patient records will be provided according to institutional guidelines. The subjects or their families will not receive any payment for participation in this study. No charge will be made for the FETO procedure being performed as part of this study.

### **10.1 Changes to the protocol and/or informed consent form**

Changes to the research covered by this protocol must be implemented by a formal protocol amendment. Protocol amendments must not be implemented without prior IRB and FDA approval. When the change(s) involve only logistic or administrative aspects of the study, the IRB only needs to be notified. During the course of the study, in situations where a departure from the protocol is unavoidable, the Investigator will contact the FDA for approval. Except in emergency situations, this contact should be made before implementing any departure from the protocol.

### **10.2 Withdrawal of informed consent**

Withdrawal of consent from a study means that the subject does not wish to receive further protocol-required therapies or procedures, and the subject does not wish to or is unable to continue further study participation in the study. The investigator is to discuss with the subject appropriate procedures for withdrawal from the study.

## **11.0 TRIAL MONITORING PROCEDURES**

### **11.1 Institutional Monitoring**

The study will be monitored by the Fetal Therapy Board at Texas Children's Hospital. The Fetal Therapy Board is an institutional board established to examine ethical and clinical aspects of this type of procedures. The Board provides written concurrence after cases are reviewed to proceed with these activities. None of the members of the Fetal Therapy Board are professionally involved in the cases under consideration. The Board membership is comprised of physicians who have the education, training and expertise needed to monitor this protocol and data as well as a medical ethicist.

### **11.2 Written Monitoring Procedures**

Case report forms are utilized to record study related data, including any procedural complications such as failed balloon placement or failed balloon retrieval, as well as surgical or anesthesia complications. Summary statistics of these data will be reviewed by the Fetal Therapy Board on an annual basis.

Maternal and neonatal outcomes will be recorded. Neonatal outcomes will include survival of the fetus, short-term measures of neonatal pulmonary morbidity, including the need for extracorporeal membrane oxygenation and the duration of neonatal ventilatory support and administration of supplemental oxygen; gastrointestinal morbidity; neurologic morbidity; survival to discharge from the hospital; and the duration of hospitalization. Assessments of other measures of long-term morbidity, including the need for supplemental oxygen, rates of recurrent infection, the need for repeated hospitalization, as well as neurodevelopmental outcomes, will be performed.

Maternal morbidity will also be assessed in terms of incidence of preterm delivery (spontaneous or indicated), cesarean section rate, length of hospitalization after the FETO procedure, length of hospitalization after balloon removal, post procedure vaginal bleeding, incidence of placental abruption, incidence of post-procedure rupture of membranes, incidence of oligohydramnios, and incidence of chorioamnionitis.

The Fetal Therapy Monitoring Board will monitor this study to ensure that the investigation is in accordance with the principles of Good Clinical Practice and that the investigators follow the protocol without any major deviations. The Fetal Therapy Monitoring Board will follow the progress of the trial including patient recruitment, data collection, management, and patient/infant outcomes.

The Fetal Therapy Monitoring Board will also review the annual and final IDE progress reports prior to submission to the FDA.

### **11.3 Monitoring, Audits and Inspections**

The Investigator will assure that local study staff cooperate with monitoring and audits. The Investigator agrees to allow auditing of all essential clinical study documents and inspection by the FDA or other appropriate regulatory authorities. Auditing visits will be scheduled with the appropriate staff at mutually agreeable times as applicable.

## **12.0 REPORTING REQUIREMENTS**

### **12.1 Registration**

The research coordinator registers all subjects in the CDH-TOTAL enrollment log. The following forms/actions are completed:

- Eligibility Checklist
- Informed Consent
- Case Report Form (CRF)

As part of the randomization process, patient data are entered in the centralized electronic database at [www.eurocdh.org](http://www.eurocdh.org).

### **12.2 Each Case**

There will be a report generated on each case within 2 days of each procedure and within 90 days of delivery setting forth the circumstances and outcomes of mother and baby. If there are no serious adverse events, this information will be reported at the time of the annual IDE report.

### **12.3 Access to Original Records**

Regulatory authorities expect that monitors, auditors, and representatives of national and international government regulatory agency bodies have access to original source documentation to ensure data integrity. "Original" in this context is defined as the first documentation of an observation and does not differentiate between hard-copy and electronic records.

### **12.4 Records Retention**

Health Insurance Portability and Accountability Act of 1996 - The Investigator agrees to comply with all applicable federal, state, and local laws and regulations relating to the privacy of subjects' health information, including, but not limited to, the Standards for Individually Identifiable Health Information, 45CFR Parts 160 and 164 (the Health Insurance Portability and Accountability Act of 1996 privacy regulation). The Investigator shall ensure that study subjects authorize the use and disclosure of protected health information in accordance with the privacy regulations of the Health Insurance Portability and Accountability Act.

### **12.5 Data Security**

Access to the data will be strictly controlled.

### **12.6 Storage**

Investigational devices must be received by a designated person at the study locations, handled and stored safely and properly, and kept in a secured location to which only the investigator and designated staff have access to. Upon receipt, all Investigational Devices should be stored in a locked and secured location.

The investigator or designated staff must maintain an accurate record of the shipment and use of the research system in an accountability ledger. Monitoring of the study accountability will be performed periodically and at the completion of the trial.

Medical records of research study participants are securely stored according to federal and legal requirements.

## **13.0 REGULATORY REQUIREMENTS**

### **13.1 Ethical conduct of the study and regulatory review**

The Investigator agrees to adhere to the instructions and procedures described in the protocol and to conduct the study in accordance with the Code of Federal Regulations (21 CFR Parts 11, 50, 54, 56, 312, 314, and 320), which originate from the ethical principles laid down in the current revision of the Declaration of Helsinki, GCP, and policies and procedures as outlined by the ethical requirements for IRB review and informed consent forms.

A copy of the protocol, proposed informed consent form and other written subject information, must be submitted to the IRB for written approval before recruitment of subjects into the study and shipment of investigational devices can begin.

The Investigator must submit and, where necessary, obtain approval from the IRB for all subsequent protocol amendments and changes to the informed consent document. Subjects who may have already been consented with the older consent form and for whom an amended consent form is relevant must be re-consented using the approved, amended forms. The investigator is to notify the IRB of deviations from the protocol or serious adverse events occurring at the site and other adverse event reports received from the device manufacturer (if applicable), in accordance with local procedures.

The Investigator is responsible for obtaining annual IRB approval /renewal throughout the duration of the study.

### **13.2 Study Management**

The Investigator will assure proper implementation and conduct of the study will be performed according to the currently approved study protocol.

### **13.3 Training of study site personnel**

The Investigator will assure research activities, including those study-related duties delegated, will be performed by appropriately qualified individuals. The Investigator will assure that study staff will demonstrate due diligence in recruiting and screening study patients.

### **13.4 Financial Disclosure**

Participating Investigators will provide a signed Financial Disclosure Form and Investigator Agreement.

### **13.5 Confidentiality**

All information provided by and all data and information generated as part of the study (other than a subject's medical records) will be kept confidential by the Investigator and other site staff. This information and data will not be used by the Investigator or other site personnel for any purpose other than conducting the study. These restrictions do not apply to the following:

- 1) Information that becomes publicly available through no fault of the Investigator or site staff;
- 2) Information that must be disclosed in confidence to an IRB solely for the evaluation of the study results;
- 3) Information that must be disclosed in order to provide appropriate medical care to a study subject; or
- 4) Study results that may be published.

## **Appendix A: Medications Used in this Protocol**

### **Mother:**

#### **Balloon placement and removal:**

- Cefazolin 2 gm IV x1
- Clindamycin 900 mg IV
- Azithromycin 500 mg IV
- Indomethacin (50 mg orally)
- Nifedipine (10 mg orally)
- Chlorprocaine 2% (11mg/kg/dose to a maximum of 800 mg)
- Ropivacaine (2.5 mg/kg/dose to a maximum of 300 mg)
- Marcaine (0.25% local anesthesia) with intravenous sedation of either Fentanyl IV or Remifentanyl IV sedation
- Betamethasone (12 mg IM, 2 doses given 24 hours apart) may be given to the mother preoperatively to improve fetal lung compliance prior to removal only.

#### **Post-Surgery after balloon placement and removal:**

- Postoperative tocolysis will be given as needed with either nifedipine (10 mg every 4 hours orally) or indomethacin (25 mg every 6 hours orally) for a maximum of two days

### **Neonate:**

#### **Balloon placement and removal:**

- Fentanyl 15 mcg/kg narcotic, Atropine 20 mg/kg anticholinergic and Vecuronium 0.1 mg/kg Muscle relaxant given as one time intramuscular injection
- 1L isotonic solution

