## 6.4.2 Anesthesia

The procedure will be performed under spinal anesthesia (2% Chloroprocaine 11mg/kg/dose for a maximum of 800mg, Ropivacaine 2.5mg/kg/dose for a maximum of 300 mg) or local anesthesia (0.25% Marcaine) with intravenous sedation (Fentanyl or Remifentanyl). Regional anesthesia choices will be made by the attending anesthesiologist according to standard of care.

The fetus will receive an intramuscular injection of narcotic, anticholinergic (Fentanyl 15 mcg/kg and Atropine 20 mcg/kg) and a muscle relaxant (Vecuronium 0.1mg/kg) into her buttocks or any extremity using a 22G needle that passes through the maternal abdominal and uterine walls in order to provide muscle relaxation, sedation, and analgesia to the fetus.

Depending on the amniotic fluid volume in the uterus an amnioinfusion using a maximum of 1L normal saline given by manual injection may or may not be employed to optimize access to the fetal nose and mouth.

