#### **6.5 Balloon Removal**

Balloon retrieval will be planned at between 34+0/7 and 34+6/7 weeks; at the discretion of the FETO center.

In the event of a patient relocating after having the balloon placed, despite having committed to remain in the area during consent process, she will be asked to return for the removal. Every effort to make arrangements for her to be managed by the nearest center capable of an EXIT procedure

or balloon retrieval (San Francisco or Philadelphia) will be made.

The optimal method for balloon retrieval (fetoscopic versus ultrasound guided percutaneous) will be decided case by case by the FETO team based on fetal position and fetal lung response.

Betamethasone (12 mg IM, 2 doses given 24 hours apart) will be given to the mother preoperatively to improve fetal lung compliance prior to removal if indicated.

Anesthesia, sedation, and tocolysis for the balloon retrieval will be as described above for the balloon placement.

Endoscopic balloon removal:

- As with placement of the balloon, fetoscopic/endoscopic retrieval will use a 9-12 Fr Teflon cannula loaded with a pyramidal trocar that is inserted into the amniotic cavity.
- A Storz endoscope or Storz fetoscope will be passed through the cannula into the amniotic fluid and maneuvered into the fetal larynx as noted above.
- The balloon will be visualized, punctured, grasped, and removed.
- The fetoscope/endoscope and cannula will be then removed.

Ultrasound guided balloon removal:

- Using a 22G needle and continuous ultrasound guidance the balloon will be punctured.
- The deflated balloon will be flushed from the trachea by the egress of pulmonary secretions distal to the occlusion. Recovery post balloon removal:

- The mother will then recover in the usual way and be discharged once stable.
- After removal of the balloon, patients will have the choice of delivering at Texas Children's Hospital Pavilion for Women with the CDH managed and repaired at TCH, or returning to their obstetrician for delivery with subsequent repair of the CDH by the pediatric surgeons at their referring facility.
- Given the severity of the CDH, the baby will need to be delivered in a facility that has the capability of immediate pediatric surgery services.

Balloon retrieval reattempts:

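### The fetal atropine dose in Appendix A is 1000 times the dose in section 6.4.2, and the two must be reconciled

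*Combined protocol and SAP*

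**What the plan says.** Two places in the protocol give the fetal drug regimen.

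- **Section 6.4.2 (Anesthesia)** names the recipient and the route: "The fetus will receive an intramuscular injection of narcotic, anticholinergic". The doses are "Fentanyl 15 mcg/kg and Atropine 20 mcg/kg", together with "a muscle relaxant (Vecuronium 0.1mg/kg").
- **Appendix A**, under the heading for the neonate and the sub-heading for balloon placement and removal, lists the same three drugs: "Fentanyl 15 mcg/kg narcotic", "Atropine 20 mg/kg anticholinergic" and "Vecuronium 0.1 mg/kg Muscle relaxant given as one time intramuscular injection".

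Section 6.5 carries the section 6.4 regimen over to balloon removal: "Anesthesia, sedation, and tocolysis for the balloon retrieval will be as described above for the balloon placement". No other part of the protocol states an atropine dose, and nothing says which text prevails if the body and the appendix differ.

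**The concern.** The same drug appears with the same number and two different units. Both instructions cannot be followed, and the gap is three orders of magnitude in a fetus.

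Appendix A is the only place where the protocol collects its drugs in one list, so staff could plausibly use it to prepare or check doses. Section 13.1 binds the investigator to the procedures described in the protocol, so a wrong unit in that list is more than a cosmetic error. A FETO-arm fetus may be exposed to it twice, at placement and again at retrieval.

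The heading adds some confusion. Appendix A files the injection under the neonate, while section 6.4.2 gives it to the fetus. A reader could take the appendix line for a separate postnatal dose.

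**Working it through.** **Step 1: is it the same injection?** The two entries side by side:

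| Item | Section 6.4.2 | Appendix A | Ratio, appendix to section 6.4.2 |
|---|---|---|---|
| Recipient label | Fetus | Neonate | – |
| Occasion | Placement; removal through section 6.5 | Placement and removal | – |
| Route | Intramuscular | Intramuscular, one time | – |
| Fentanyl | 15 mcg/kg | 15 mcg/kg | 1 |
| Vecuronium | 0.1 mg/kg | 0.1 mg/kg | 1 |
| Atropine | 20 mcg/kg | 20 mg/kg | see step 2 |

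The drugs, drug classes, route and occasion match, and so do two of the three doses. Planned placement and removal are in-utero procedures (sections 6.4.3 and 6.5). The appendix line is therefore the fetal injection, despite its heading. The protocol contains no separate neonatal atropine regimen that could explain the difference.

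**Step 2: size of the discrepancy.** Convert to a common unit:

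- Appendix A: 20 mg/kg × 1000 mcg/mg = 20,000 mcg/kg.
- Section 6.4.2: 20 mcg/kg.
- Ratio: 20,000 / 20 = 1000.

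**Step 3: absolute doses.** The protocol gives no fetal weight, so a range of 1.0 to 2.5 kg is assumed. Dose = weight × dose per kg:

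| Assumed weight | Section 6.4.2 | Appendix A |
|---|---|---|
| 1.0 kg | 0.02 mg | 20 mg |
| 1.5 kg | 0.03 mg | 30 mg |
| 2.0 kg | 0.04 mg | 40 mg |
| 2.5 kg | 0.05 mg | 50 mg |

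The ratio of 1000 does not depend on the assumed weight.

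**Step 4: effect of the correction.** With Appendix A at 20 mcg/kg, the atropine ratio becomes 20 / 20 = 1, and all three drugs agree between the two places.

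**The case against.** The strongest reply concerns likelihood, since the contradiction itself cannot be denied. Section 6.4.2 is the treatment instruction: it states recipient, route, injection site and needle. Section 6.5 refers back to that text and not to the appendix. Apart from the table of contents, nothing in the protocol sends the reader to Appendix A. Someone who follows the procedure sections reaches 20 mcg/kg on both occasions. The appendix figure looks like mg typed for mcg, and an anesthesia team might well question a dose of 20 to 50 mg. The documents mention no order set or worksheet derived from the appendix.

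These points lower the probability of harm and do not resolve the conflict. No precedence rule is stated, and the protocol describes no dose check that would catch the error. The discretion given to the anesthesiologist in section 6.4.2 covers regional anesthesia for the mother, not the fetal dose. It is fair that the appendix's use in practice is an assumption, that the check of derived materials applies only if such materials exist, and that the recipient label is a minor matter beside the unit.

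The text was read from PDF by a program, so a misread unit cannot be wholly excluded without the source file. It is unlikely: mcg is read correctly for fentanyl on the same appendix line, and for both drugs in section 6.4.2.

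**Conclusion.** The concern holds. The protocol gives two atropine doses for one fetal injection that differ by a factor of exactly 1000, and it does not say which is right. The factor follows from the units alone. The absolute doses (0.02 to 0.05 mg against 20 to 50 mg) rest on the assumed weight range of 1.0 to 2.5 kg.

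The pattern of the entries makes 20 mcg/kg the more plausible intention, but the documents do not establish it, so the sponsor must confirm the value. Nothing here shows that the appendix dose was given to anyone. The point is an inconsistency in a drug dose, with no bearing on sample size, error rates, endpoints or analysis. It must be fixed because the conflict is certain and the potential consequence is grave, even if the route to harm is indirect.

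**What to change.** 1. Confirm the intended dose with the responsible anesthesia and fetal-medicine staff, and state it with one unit in both section 6.4.2 and Appendix A. If 20 mcg/kg is confirmed, only the appendix unit changes.
2. Label the recipient as the fetus in both places, so that the appendix line cannot be read as a postnatal dose.
3. If any order set, preparation sheet or drug worksheet was built from Appendix A, check it against the confirmed dose.
4. Compare the appendix line once with the source file, to rule out a reading error.

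The cost is a one-line correction with a changed label, made through the amendment process in section 10.1, and a short check of derived materials. No design or analysis element needs to change.

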#### **If Pre-term delivery:**

- Exogenous surfactant (Exosurf Neonatal, Glaxo Wellcome) administered at a dose of 3 ml/kg of body weight

